6.5 Analysis Visit Window

Data will be analyzed by scheduled visits, where appropriate. Data collected out of the prescribed timing window will be analyzed as scheduled (i.e., at intended visits). Data that are collected from an unscheduled visit will not be included in the by-visit summary tables but will be presented in the listings. However, data collected at an unscheduled visit will also be considered for toxicity grading, in particular, for laboratory assessments. Additionally, both unscheduled and out of window imaging assessments will be included in the efficacy analysis.

6.6 Handling of Partial Dates for Adverse Events

When determining treatment-emergent adverse events (TEAEs), partial dates will be handled as follows.

- If the day of the month is missing, the onset day will be set to the first day of the month unless it is the same month and year as study treatment. In this case, the onset date will be assumed to be the first dose date of treatment.
- If the onset day and month are both missing, the day and month will be assumed to be 1 January, unless the event occurred in the same year as the study treatment. In this case, the event onset will be coded to the first dose date of treatment to conservatively report the event as treatment-emergent.
- A missing onset date will be coded as the first dose date of treatment. If the resulting onset date is after a reported date of resolution, the onset date will be set equal to the date of resolution.
- A partially missing resolution date will be conservatively imputed as the latest date in the range of missing date element(s) (for example 2020-10-31 if the date is 2020-10-UNK), date of last dose + 90 days, day of study discontinuation, or death, whichever comes first.

Data listings will present the partial date as recorded in the electronic case report form (eCRF).

6.7 Handling of Partial Dates for Medications

When determining prior or concomitant medications, partial start dates of prior and concomitant medications will be assumed to be the earliest possible date consistent with the partial date.

 Medication start dates with a missing day and non-missing month will be assumed to have occurred on the first day of the non-missing month, except for medications occurring in the first month of dosing, in which case the date will be one day before the first day of dosing.

Confidential Page 14 of 30

- Medication start dates with missing day and month will be assumed to have occurred on the first day of the non-missing year (i.e., 1 January), except for medications occurring in the first year of dosing, in which case the date will be the informed consent date.
- For post anti-cancer medications only, if both Month and Day are missing, then the start date will be set to December 31 or the end date of this medication, whichever occurs first.
- For post anti-cancer medications only, if only Day is missing, then the start date will be set to the last day of the month or the end date of this medication, whichever occurs first.
- Medications that are not ongoing and have a medication stop date with a missing day and non-missing month will be assumed to have stopped on the last day of the non-missing month.
- Medications that are not ongoing and have a medication stop date with a missing month will be assumed to have stopped on the last day of the non-missing year (i.e., 31 December).

When imputing start date of a medication ensure that the new imputed date is sensible, i.e., is prior to the end date. If start date and/or end date of a prior/concomitant medication is completely missing, do not impute.

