8.7.1 Best Overall Response and Objective Response per RECIST 1.1

Best overall response (BOR) will be derived from time-point RECIST 1.1 assessments by investigators. In the primary analysis, BOR will be evaluated over all on-study time-point assessments recorded before start of a new anti-cancer therapy, in consideration of RECIST 1.1 definition: "The best overall response is the best response recorded from the start of the study

Confidential Page 26 of 30

Statistical Analysis Plan 07 Oct 2021

treatment until the end of treatment taking into account any requirement for confirmation. On occasion a response may not be documented until after the end of therapy so protocols should be clear if post-treatment assessments are to be considered in determination of best overall response" (Eisenhauer et al 2009). Since all assessments are considered for BOR, the confirmed objective response or stable disease (SD) may occur after a transient time-point progressive disease (PD) assessment(s).

In the secondary analysis, conducted for sensitivity evaluation, an alternative, more conservative approach will be used. BOR will be evaluated only over time-point assessments until first observed PD, as initially proposed in RECIST 1.0 (Therasse et al 2000).

Confirmation of objective response (complete response [CR] or partial response [PR]) is required for respective BOR of CR or PR. Confirmation must be obtained at a subsequent assessment at least 4 weeks apart. In case of CR, the confirmatory assessment must be performed at a consecutive assessment, except for intercurrent non-evaluable assessments.

In case of PR, confirmatory assessment after initial CR/PR may be obtained a) in the primary analysis any time at least 4 weeks apart from the initial assessment, without restrictions on intercurrent assessment b) in the secondary analysis, any time after 4 weeks and after at most 1 intercurrent assessment of non-evaluable (NE) or SD.

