For patients who did not fulfill requirements for BOR of CR or PR as described above, BOR of SD is defined, in the primary analysis, as i) initial time point assessment(s) of SD, PR, CR without PD at a minimum interval of 39 days (6 weeks-3 days), disregarding NE assessments and/or ii) unconfirmed PR or CR any time at initial evaluation, without PD at a minimum interval of 39 days and/or iii) durable SD following transient PD: at least 2 assessment(s) of SD, PR, CR (ignoring intercurrent NE assessments) at least 39 days (6 weeks-3 days) apart and without new PD within 84 days, counting time from the last transient PD assessment. Subjects who have a response of PR or CR with no subsequent tumor assessments will be assigned a BOR of SD and will be flagged in listings. In the secondary analysis, BOR evaluation of SD is only considered based on only criterion i) above. For BOR of SD without confirmation, the stable disease must meet the criterion of minimum time of 39 days.

For patients with time point assessment(s) of PD, excluding any transient PDs (PD followed by confirmed objective response or durable SD) and who do not satisfy criteria for BOR of CR, PR, and SD described above, the BOR assessments in the primary analysis will be PD. In the secondary analysis, a similar definition will be used but without excluding transient PDs.

Finally, BOR of NE will be assigned where there are either no evaluable time point assessments at all or first time point assessment(s) of SD was before minimum interval of 39 days without evaluable assessments preformed after 39 days.

The objective response rate (ORR) is the percentage of subjects with a BOR of PR or CR (i.e., objective response). The analysis of ORR will include confirmed responses and unconfirmed responses for both primary and alternative analyses. Subjects with missing tumor response status assessment will be counted as non-response (that is, subjects without any follow-up assessment) will be counted in the denominator for ORR.

BOR and ORR will be listed for Safety Analysis Set as available using primary and alternative definitions. For confirmed response, duration of response will be listed (see Section 8.7.2). The listings of time-point response will include assessments of target lesion, non-target lesions, and

Confidential Page 27 of 30

new lesion data, as well as percentage change from baseline in the sum of diameters of target lesions.

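### Partial start dates of later anti-cancer therapy are set to the latest consistent date, so scans taken on that therapy can count towards the study drug's response rate

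*SAP*

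**What the plan says.** SAP 6.7 handles partial start dates in two opposite directions. For other medications, "partial start dates of prior and concomitant medications will be assumed to be the earliest possible date consistent with the partial date". For anti-cancer medication given after study drug the rule is reversed. If month and day are missing, "the start date will be set to December 31 or the end date of this medication, whichever occurs first"; if only the day is missing, "the start date will be set to the last day of the month or the end date of this medication, whichever occurs first". Stop dates are also pushed late: a finished medication whose stop month is unknown is given the last day of the year.

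The date then acts as a cut-off. In the primary analysis of SAP 8.7.1, "BOR will be evaluated over all on-study time-point assessments recorded before start of a new anti-cancer therapy". From this, "The objective response rate (ORR) is the percentage of subjects with a BOR of PR or CR". The section requires a response to be confirmed at least 4 weeks later, but it also states: "The analysis of ORR will include confirmed responses and unconfirmed responses for both primary and alternative analyses". SAP 8.7.2 (duration of response, DOR) and 8.7.6 (progression-free survival, PFS) use the same cut-off and disregard scans and deaths after it. SAP 6.5 admits unscheduled and out-of-window scans to the efficacy analysis.

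Imaging continues after study drug in subjects who stop without progression: every 12 weeks for up to 2 years from first dose in Protocol 3.5, and every 6 weeks or per a disease-specific schedule in Protocol 5.7.1. The two sections need reconciling. Neither names the start of another therapy as the end of imaging. Protocol 5.1.5 follows survival by phone every 3 months and also tracks the start of another cancer therapy.

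**The concern.** The start of new therapy is the only cut-off that the primary response analysis states between scans reflecting AGEN1884 and scans reflecting the next treatment. If it is placed later than the truth, every scan in the gap is treated as a study-drug scan, and a response to the next therapy can enter best overall response (BOR) and ORR. Partial dates are plausible where the start of later therapy is learned by phone. The trial is open-label and single-arm, so no comparator would share and cancel the error. With about 20 subjects in the hepatocellular carcinoma (HCC) group, one misplaced response is visible in the reported rate. The SAP gives no analysis that varies the imputed date.

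**Working it through.** The plan attaches no figure to this rule, so there is none to reproduce. I checked the direction first, then the size.

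**Inputs.** Scan interval q = 42 days (Protocol 5.7.1) or 84 days (Protocol 3.5). Confirmation at 28 days or more (SAP 8.7.1). N = up to 60, about 20 HCC and 40 non-HCC (SAP 3.2). Two-sided 95% Wilson intervals (SAP 8.1). Length of the unknown period L = 365 days (month and day missing) or 31 days (day missing).

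**Assumptions not in the documents.** The true start is uniform over the unknown period, scan timing is uniform, imaging continues, and the end-date cap does not bind.

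**1. Direction.** The imputed date is the smaller of the latest consistent date and the end date. Neither can precede the true start, and an imputed end date is itself late. So the imputed date is never early. Scans wrongly admitted come after all those correctly admitted. They can supply or confirm a response but cannot undo one. ORR can only stay the same or rise.

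**2. Lateness.** Maximum L − 1 and mean (L − 1)/2: 364 and 182 days with month and day missing; 30 and 15 days with the day missing.

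**3. Scheduled scans in the gap.** The maximum is (L − 1)/q rounded down or up, depending on scan timing. The mean is (L − 1)/(2q).

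| Missing | Interval | Maximum | Mean | At least 1 | At least 2 |
|---|---|---|---|---|---|
| Month and day | 42 days | 364/42 = 8.7, so 8 or 9 | 182/42 = 4.3 | 94% | 83% |
| Month and day | 84 days | 364/84 = 4.3, so 4 or 5 | 182/84 = 2.2 | 88% | 65% |
| Day only | 42 days | 30/42 < 1, so 0 or 1 | 15/42 = 0.36 | 36% | 0% |
| Day only | 84 days | 30/84 < 1, so 0 or 1 | 15/84 = 0.18 | 18% | 0% |

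The percentages are for subjects who have such a date, and come from a simulation of 400,000 draws under the stated assumptions. As a check, a gap of g < q days holds no scan with probability 1 − g/q. Averaging over g = 0 to 364 gives 21.5/365 = 5.9% with no scan at 42 days and 42.5/365 = 11.6% at 84 days, hence 94% and 88%.

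**4. What a scan in the gap can do.** A response and its confirmation need two scans at least 28 days apart. With only the day missing, scheduled scans cannot supply both. One scan can still confirm an earlier response or add an unconfirmed one.

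**5. Effect on ORR per misattributed responder.** 1/60 = 1.7 points, 1/40 = 2.5 points, 1/20 = 5.0 points. For x responders, with p = x/N and z = 1.96, the Wilson limits are [p + z²/2N ± z√(p(1 − p)/N + z²/4N²)] / (1 + z²/N).

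- N = 20: x = 0 gives 0.0% (0.0 to 16.1); x = 1 gives 5.0% (0.9 to 23.6); x = 2 gives 10.0% (2.8 to 30.1).
- N = 60: x = 0 gives 0.0% (0.0 to 6.0); x = 1 gives 1.7% (0.3 to 8.9); x = 2 gives 3.3% (0.9 to 11.4).

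**6. DOR and PFS.** A later cut-off can lengthen a censored time. It also admits progressions and deaths that would otherwise be disregarded, turning censored times into events. The net direction is not determined.

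**The case against.** **The after-progression route is narrow.** Because the primary BOR accepts a confirmed response after a transient progression, a reader might infer that subjects who progress, move to another drug and respond to it would often be counted as AGEN1884 responders. The documents do not support that. Post-treatment imaging is planned for subjects who stop without progression (Protocol 3.5, 5.7.1). Imaging in those treated beyond progression ends with treatment (Protocol 3.7). The Final Safety Visit is brought forward if new therapy starts first (Protocol 5.1.4). As far as Table 10 can be read, survival follow-up has no imaging. A progression is set aside only for a confirmed response or durable stable disease, so at least two later scans are needed. The secondary BOR analysis stops at first progression and closes this route. All of this stands. What remains is new therapy begun before progression, which the secondary analysis does not catch, and unscheduled scans.

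**The long window is a worst case.** It needs month and day both unknown, a true start on 1 January, no binding end date and study imaging throughout another treatment. Contact every 3 months would usually place the start more closely than a year. This also stands. The end-date cap is weak, however: it does nothing for ongoing therapy or for a stop date known only to the year.

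**The reversed rule has a purpose.** Under the general rule, a later therapy with month and day missing in the first dosing year would be dated to informed consent, before any study drug. That justifies a lower limit on the date, not the latest date.

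**The stakes are limited.** Efficacy is secondary and called preliminary, the sample size is not inferential, and no ORR threshold is stated. Protocol 4.5 also bars other anti-cancer therapy during the study, although the SAP's own cut-off anticipates it.

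**Conclusion.** The concern holds for ORR. A stated rule can place scans taken on later therapy inside the study-drug window, and for ORR the error has one direction. The exposure is mainly in subjects who stop study drug without progression, continue imaging and start another therapy with a partial date, plus unscheduled scans.

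The effect is small if only days are missing: at most one scheduled scan, in about 36% (6-weekly) or 18% (12-weekly) of such subjects. It could matter if months are missing too. Each misattributed responder adds 1.7 points at N = 60 and 5 points at N = 20. The total cannot be stated, because the documents do not give the number of partial dates or of scans taken on later therapy. The percentages rest on uniform timing, continued imaging and no binding cap.

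A reader might also infer that the rule flatters DOR and PFS. The documents do not support a fixed direction there, because progressions and deaths inside the gap become events. The point does not touch the primary safety and pharmacokinetic objectives.

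**What to change.** Derive one new-therapy start date per subject: the earliest date consistent with the known parts, but not before the day after the last study dose. Use it as the cut-off for BOR, ORR, disease control rate, DOR and PFS alike, so that no subject has different dates for different endpoints. Repeat these analyses with the current latest-date rule as a sensitivity bound, and report how many subjects have a partial date and of which kind.

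Provided the true start follows the last study dose, the imputed date cannot then fall after it, and the window for wrongly credited scans drops from up to 364 or 30 days to 0.

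The cost is SAP wording, one derivation and one repeat run. The statistical cost is that some valid scans before the true start leave the main analysis. When only the year is known this may be several, possibly including a genuine response or its confirmation. The main analysis would then lean towards a lower ORR, and the difference from the sensitivity bound shows how much depends on the imputation.

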6.9 Handling of Partial Dates for Other Data

Other data (such as disease history) with partial dates will be listed as collected. For calculation of time intervals, the dates will be imputed with the first day of the month (if the day is missing) or with 1 January (if both day and month are missing).

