8.5.4 Prior Cancer Therapies and Procedures

Prior cancer systemic therapies will be summarized and listed including:

- Any prior cancer medication
- BOR on the last treatment/therapy before enrollment
- Time from last day of last treatment to first dose date (months), defined as (first dose date date of last day of last treatment + 1)/30.4375

Anti-cancer therapies will be coded using WHODrug-B3 September 2019. Prior anti-cancer treatment, radiotherapies, and surgeries will be listed.

The Safety Analysis Set will be applied for this analysis.

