8.5.5 Prior and Concomitant Medications

Prior and concomitant medications will be summarized and listed in the Safety Analysis Set. Medications will be coded using WHODrug-B3 September 2019. The count and percentage of subjects who took concomitant medications will be tabulated by Anatomical Therapeutic Chemical (ATC) level 2 and PT. Prior medication is defined as any non-study medication started before the first dose of study drug. Concomitant medication is defined as any non-study medication that was dosed on or after first study drug administration.

Confidential Page 19 of 30

Agenus Inc. Statistical Analysis Plan for Study C-500-01 Phase 2

A prior medication could also be classified as "both prior and concomitant medication" if the end date is on or after first dose of study drug. In the listing, it will be indicated whether a medication is prior-only, concomitant-only, or both prior and concomitant medication.

The Safety Analysis Set will be applied for this analysis.

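### SAP 6.7 does not tie imputed medication starts to the onset of the AE treated, nor imputed stops of prior cancer therapy to the first study dose, which distorts some descriptive summaries

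*SAP*

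**What the plan says.** **Start dates (SAP 6.7).** A partial start "will be assumed to be the earliest possible date consistent with the partial date". With the day missing this is the first of the month, unless that is the month of first dosing, "in which case the date will be one day before the first day of dosing". With day and month missing it is 1 January, or the consent date if the year is the first year of dosing. An imputed start must precede the drug's own end date.

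**Stop dates (SAP 6.7).** A drug that is not ongoing and lacks the stop day "will be assumed to have stopped on the last day of the non-missing month"; with the month missing, the stop is 31 December. No upper limit is given. By contrast, SAP 6.6 limits imputed AE resolution dates by last dose plus 90 days, study discontinuation or death.

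**Where the dates are used.**
- SAP 8.6.2, cluster summaries: the percentage of patients treated counts ATC groups H01, H02 and H03 only if the drug was indicated for an AE, began after that AE's onset, and began no later than its resolution or 21 days from onset.
- SAP 8.5.5: a prior drug is also concomitant "if the end date is on or after first dose of study drug".
- SAP 8.5.4: time since last therapy is first dose date minus last treatment day, plus 1, divided by 30.4375.
- SAP 6.9, for other data such as disease history: "For calculation of time intervals, the dates will be imputed with the first day of the month", or 1 January if the month is also missing.

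**The concern.** Taking the earliest start and latest stop is a sensible default when the question is whether a drug might have been taken on study. It does not suit a rule that asks whether a drug began after an event, or how long ago a therapy ended.

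In the first case the imputation pushes the drug to the wrong side of the AE and removes it from the count of treated patients. Those percentages describe how immune-mediated toxicity was managed, in a study whose primary endpoint is safety. In the second case, therapy that ended before the study can be listed as concomitant, although Protocol 4.5 bars other anti-cancer therapy during the study. Time since last therapy may also differ by weeks depending on whether the programmer applies 6.7 or 6.9.

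**Working it through.** The plan states no figure to reproduce. The check applies the SAP rules to illustrative records, then to every calendar day of 2019 and 2020.

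**Assumptions, not in the documents:** dates are uniform over the year; prior therapy ends 14 to 42 days before first dose (the protocol's 2 to 6 weeks); the drug for an AE begins 0 to 7, 0 to 14 or 0 to 21 days after onset (21 is the limit in 8.6.2).

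**1. Start dates, single records**
- AE onset 18 June; steroid start recorded as June, day unknown. Imputed start 1 June, 17 days before the AE. Not counted.
- First dose 4 May; AE onset 18 May; steroid start recorded as May, day unknown. Imputed start 3 May. First dose minus 1 precedes every onset on or after first dose, so such a record always fails.
- AE onset and drug start both lack the day, both in the first dosing month. SAP 6.6 sets the AE to first dose and 6.7 sets the drug to the day before. The drug again comes first.

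**2. Start dates, all calendar days (day missing, first-of-month rule)**

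| Lag from AE onset to drug | Imputed start before onset |
|---|---|
| 0 days | 97% |
| 0–7 days | 85% |
| 0–14 days | 74% |
| 0–21 days | 62% |

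**3. Stop dates, single record.** First dose 20 March 2020; true stop 3 March; recorded as March, day unknown.
- True interval by the 8.5.4 formula: 20 − 3 + 1 = 18 days.
- SAP 6.7 (stop 31 March): 20 − 31 + 1 = −10 days, and the drug is both prior and concomitant.
- SAP 6.9 (stop 1 March): 20 − 1 + 1 = 20 days.
- Only the year recorded, under 6.7 (31 December 2020): −285 days.

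**4. Stop dates, all calendar days, gaps 14–42 days**
- Day missing: imputed stop on or after first dose in 16%. By gap: 54% at 14 days, 31% at 21, 8% at 28, 0% at 42.
- Month missing: on or after first dose in 92%.
- Day missing, 6.7 applied to 8.5.4: interval below zero in 12.7%. Under 6.9 it is never zero or negative.

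**5. Scale.** The share of partial dates is not stated, so a range is shown.

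| Share of records partial | AE-drug records lost (share × 62% to share × 85%) | Subjects with a day-missing stop reclassified (share × 0.163 × 60) |
|---|---|---|
| 1% | 0.6–0.9% | 0.1 |
| 5% | 3.1–4.3% | 0.5 |
| 10% | 6.2–8.5% | 1.0 |

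If it were the month that was missing in 5% of subjects, 0.05 × 0.923 × 60 gives about 2.8. The figure of 60 is the Phase 2 maximum. PD-1/PD-L1 naïve subjects need not have a gap of 14 to 42 days, so the last column is a rough upper guide.

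**6. Which rule suits the 8.5.4 interval.** Capping the stop at the day before first dose and using that date in 8.5.4 gives first dose − (first dose − 1) + 1 = 2 days in every case that the cap touches. In those cases the mean absolute error is 18 days, against 5 under 6.9. Over all gaps the first-of-month rule is no more accurate than the month-end rule (mean error 14.7 days for each). Its advantages are that the interval stays positive and that it does not manufacture a 2-day washout. Its error always lengthens the interval, so imputed values need a flag.

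**The case against.** **SAP 6.9 may already govern 8.5.4.** Prior cancer treatments are collected as medical history (Protocol Table 10, footnote a) and summarised apart from other medications, and 6.9 speaks of time intervals. That is a fair reading, so the negative interval is conditional. But 6.7 covers prior medications and makes a separate rule only for post-study anti-cancer drugs, so either section can be applied. The reclassification in 8.5.5 does not depend on this choice.

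**The imputation is deliberately cautious.** True for detecting concomitant exposure. It works the other way in the 8.6.2 filter, where an earlier start removes the treatment.

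**The loss is per record, but the table is per patient.** This stands. A patient is lost only if no other qualifying record has a usable date. Long steroid tapers make several records plausible, so the patient-level understatement is smaller than 62–85% of affected records.

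**Stronger readings a reader might infer.**
- That the Phase 2 population or its washout is in doubt. The 2 to 6 week interval is checked at eligibility, and refractory or naïve status comes from sponsor review of a treatment listing (SAP 8.5.3), not from imputed dates.
- That treatment of AEs is under-reported generally. The filter applies only to H01, H02 and H03 drugs in the cluster summaries. The primary irAE tables use investigator reports without it.
- That 6.7 has no bounds at all. Starts are limited by the end date, and some are anchored to first dose or consent. These anchors do not prevent the errors, and the first-dose anchor causes one of them.

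**Conclusion.** The point holds as a minor defect in the SAP. For drugs given for cluster AEs, a missing start day puts the drug before the AE in 62% to 85% of records for lags up to 21 or up to 7 days, and always in the first dosing month when onset is on or after first dose. This biases the cluster treatment percentages downward. For prior cancer therapy, about 16% of day-missing and 92% of month-missing stops make the drug also concomitant. A negative time since last therapy follows only if 6.7 is applied to 8.5.4, which the SAP leaves open.

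All these figures are conditional on a partial date and on the uniform-date and gap assumptions above. At a few percent of partial dates the absolute effect is small. No efficacy endpoint changes, because post-study anti-cancer starts have their own rule.

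**What to change.** 1. **SAP 6.7, starts.** For a medication whose recorded indication is an AE, impute a partial start as the later of the earliest date consistent with the record and the AE onset date, provided that onset lies within the recorded month or year. State in 8.6.2 that a start on the day of onset counts; otherwise the bounded date could still fail. In the enumeration this takes starts placed before onset from 62–85% to 0%.
2. **SAP 6.7, stops.** For the prior/concomitant classification only, cap the imputed stop of therapy recorded on the prior anti-cancer treatment form, and not marked ongoing, at the day before first dose. Keep the recorded partial date in the listing, so that a therapy that really ran past first dose stays visible.
3. **SAP 8.5.4.** State that the interval uses the first-of-month rule of 6.9 when the day is missing, not the capped 6.7 date, and flag imputed intervals in the listing.

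The cost is a few sentences and minor programming. The first change needs each drug to be traceable to its AE. The 8.6.2 filter already presupposes this, but the case report form is not among the documents, so the link should be confirmed before the rule is finalised.
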